Permuted block randomization with varying block sizes of 2 and 4 will be used to randomize 100 patients 1:1 to either the intervention or the control group. Random assignment will be conducted using the Statistical Analysis Software (SAS). Given the nature of the intervention, study participants and personnel will not be blinded to group allocation, but data analysts will be.

Intervention

Usual care

At discharge, patients will be provided with a written discharge prescription to be filled at their community pharmacy, and may or may not receive written or verbal instructions about changes made to therapy.

Intervention arm

At discharge, patients (and/or caregivers) will receive access to a medication management application that has been developed by the McGill Clinical and Health Informatics (MCHI) Research Group. The application will retrieve all medications prescribed to patients at discharge from an electronic form with structured data fields that has been completed by a study field coordinator using the patient's discharge prescription. The app will then generate a patient-friendly medication list and will offer a number of important features aimed at addressing barriers to adherence, including:

- **Pill identification:** This feature displays an image of a pill next to each medication in the list, with the intention of ensuring patients take the correct medications at the appropriate dosage and at the right times.
- **Drug information:** Patient-friendly monographs are provided to help patients and caregivers understand the indications for treatment, as well as the harms and benefits of their medications. Improved health literacy with respect to treatment has the potential to increase appropriate utilization of medications by patients.
- **Drug alerts:** Using prescription claims data of the 30 days post-discharge, which will be obtained from the RAMQ, this feature alerts patients to their non-adherence, such as in cases in which they have filled prescriptions that were stopped at hospital discharge, have yet to fill prescriptions for medications newly prescribed at discharge, or have been dispensed medications at the incorrect dose.
- **Daily pill reminders:** This feature reminds patients to take their medication on the day/time they are supposed to. Patients can choose whether or not they want this feature activated.

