Pharmacy claims data from the RAMQ will be used to identify community medications dispensed to participating patients in the 30 days following hospital discharge. These data will be compared with the patient's hospital discharge prescription to identify non-adherence to in-hospital medication changes. Non-adherence to in-hospital treatment changes in the 30-day post-discharge period will be defined as (1) failure to fill newly prescribed medications, (2) re-filling a previous prescription that was stopped at discharge, or (3) filling a previous prescription whose dosage was modified at discharge, but was dispensed post-discharge at the incorrect daily dose.

Data sources

Prescription claims data from the *Régie de l'assurance maladie du Québec (RAMQ)* will be used to identify prescriptions filled in the 3 months prior to admission and the 1 year following discharge.

Medications prescribed at discharge and in-hospital medication changes will be determined using patients' discharge prescriptions, which will be obtained from patients' hospital charts.

Data Analysis

Descriptive statistics will be used to summarize demographic and clinical characteristics of the study population, results of the technology assessment questionnaire, and the frequency of nonadherence events (as defined in the previous section) in the 30 days post-discharge, overall and in each study group. We will then compare, between intervention and control groups, the average number of in-hospital medication changes not adhered to in the 30-day follow-up period using the Student's t-test. All quantitative statistical analyses will be conducted using SAS version 9.4. Data from the "think aloud" protocol will be analyzed qualitatively.

[figure not shown]
Project timeline

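### A newly prescribed drug dispensed at the wrong daily dose meets none of the three non-adherence rules, so it scores 0 like a correct fill

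*Combined protocol and SAP*

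**What the plan says.** The definition is under Outcome measures, in the section on non-adherence to treatment changes. It lists three rules joined by *or*:

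- Rule 1: "failure to fill newly prescribed medications".
- Rule 2: "re-filling a previous prescription that was stopped at discharge".
- Rule 3: "filling a previous prescription whose dosage was modified at discharge, but was dispensed post-discharge at the incorrect daily dose".

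The data source is 30 days of RAMQ pharmacy claims: "These data will be compared with the patient's hospital discharge prescription to identify non-adherence to in-hospital medication changes". The Data Analysis section refers back to this definition for the event frequencies. It then compares the arms on "the average number of in-hospital medication changes not adhered to in the 30-day follow-up period using the Student's t-test", which is the only between-arm efficacy test in the plan.

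The Drug alerts item under Intervention arm says that the app alerts patients to non-adherence and gives examples. Besides the filling of stopped drugs, these are cases in which patients "have yet to fill prescriptions for medications newly prescribed at discharge" or "have been dispensed medications at the incorrect dose".

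**The concern.** Starting a drug at a stated dose is an in-hospital medication change, and the discharge prescription is the reference for judging it. If the pharmacy dispenses that drug at another daily dose, the patient is not receiving the change as prescribed, yet none of the rules records this. The event is counted as adherence in the one number on which the arms are compared.

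The count is then somewhat understated in both arms, and any difference between arms in this type of error does not enter the comparison. The alert description makes the gap more noticeable: its wrong-dose example is not confined to drugs whose dose was modified, so the app may call something non-adherence that the outcome does not.

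**Working it through.** **Step 1. Apply the three rules literally to each type of change.**

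| Change at discharge | What the claims show | Rule met | Score |
|---|---|---|---|
| New drug | Filled, correct dose | none | 0 |
| New drug | Filled, wrong dose | none | **0** |
| New drug | Not filled | 1 | 1 |
| Stopped drug | Re-filled | 2 | 1 |
| Stopped drug | Not re-filled | none | 0 |
| Dose-modified drug | Filled, correct dose | none | 0 |
| Dose-modified drug | Filled, wrong dose | 3 | 1 |

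In the second row, rule 1 fails because the drug was filled, rule 2 because it was not stopped, and rule 3 because it is not a previous prescription. No other section adds a dose rule for new drugs.

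**Step 2. Set the outcome beside the alert.** The three alert examples cover a stopped drug that is filled, a new drug that is not filled, and a wrong dose. The first two carry the same restriction as rules 2 and 1. The third, "or have been dispensed medications at the incorrect dose", lacks rule 3's restriction to previous prescriptions with a modified dose. Taken at its word, it includes the second row of the table. The list is introduced as illustrative, so it does not settle what the alert logic is.

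**Step 3. Illustrate the size.** The plan states no figure to reproduce: it gives neither the number of new drugs per patient nor a wrong-dose rate. The only documented input is the sample size, 100 patients randomised 1:1, or 50 per arm. The rest is assumed:

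- m, new drugs per patient: 2 to 4
- f, proportion of new drugs filled: 0.70 to 0.90
- w, proportion of those fills at a wrong daily dose: 0.01 to 0.10

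Uncounted events per patient = m × f × w.

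- Low: 2 × 0.70 × 0.01 = 0.014 per patient; × 50 = 0.7 per arm.
- High: 4 × 0.90 × 0.10 = 0.36 per patient; × 50 = 18 per arm.

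**Step 4. Effect on the between-arm difference.** The part of the difference that goes unseen is m₁f₁w₁ − m₀f₀w₀, where 1 is the intervention arm and 0 the control arm. It is zero if the products are equal. The documents give nothing from which to say that they differ, or in which direction.

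**Step 5. Effect of the repair.** If the dose condition also covered new drugs, the second row would change from 0 to 1 and no other row would change.

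**The case against.** **The scope may be deliberate.** For a new drug the change is starting it; for a modified drug the change is the dose. That is a coherent position and the same rules apply to both arms. But the plan does not state this reasoning, and the reference it names is the discharge prescription, which includes the dose. One could also read rule 1 as failure to fill as prescribed. The explicit dose condition in rule 3, and its absence from rule 1, argue against that.

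**The conflict with the app may be only apparent.** A reader might infer that the protocol contradicts itself, with the app treating as non-adherence what the outcome treats as adherence. The documents do not support so firm a statement. The alert text is a short feature description with illustrative examples, which line up one for one with the three rules, so the wrong-dose item may be shorthand for rule 3. The Caregiver connect item also speaks of non-adherence to treatment changes, the term that heads the outcome definition. The pharmacist's option under Pharmacy connect to report dispensing errors arises from talking with the patient and defines no outcome. This objection stands: the mismatch is possible, not established.

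**The repair does not credit corrected errors.** The alerts run on claims data, so a wrong-dose fill has already happened when an alert is issued. An error that is flagged and then corrected would still count as one event. This also stands. The extended rule would capture differences in whether wrong-dose fills occur, not in whether they are put right.

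**The size is unknown.** This stands too. At the low end of the assumed range it is less than one event per arm.

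**Conclusion.** The gap is real on the wording of the definition: a newly prescribed drug dispensed at a daily dose other than the prescribed one scores 0, and nothing elsewhere in the document changes that. It is a minor weakness in the efficacy count that is cheap to remove.

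The range of 0.7 to 18 uncounted events per arm rests entirely on assumed inputs; the true figure may be small. A reader might go further and infer that the treatment comparison is biased, or that the repair would let the trial show the app catching and correcting dose errors. Neither follows. The rules are identical in both arms and the documents contain no rates by arm. An error corrected after an alert would count the same as one never corrected.

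**What to change.** In the section on non-adherence to treatment changes, extend rule 3 to read: *dispensing, at a daily dose other than that on the discharge prescription, of a drug newly prescribed or dose-modified at discharge*. Add that each change is counted at most once.

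Leave the wording of the Drug alerts item as it is. Restricting it to new or dose-modified drugs could narrow an alert that, as written, may also cover drugs left unchanged at discharge. That would alter the intervention in order to tidy an outcome definition.

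The cost is one sentence. The claims, the discharge prescription and the daily-dose comparison are already planned for dose-modified drugs. The downside is slightly more coding and a slightly higher count in both arms. A wrong-dose fill that is later corrected still counts as one event, as the present wording of rule 3 already implies.

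This edit does not touch a separate case: a dose-modified drug that is never filled after discharge also scores 0 under the literal rules.

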Evaluation of a Mobile Application to Enhance Medication Management Following Hospital Discharge

Research Protocol

April 26, 2019

[figure not shown]
NCT04676165

Background

Adverse drug events (ADEs) are among the leading causes of death in North America^{1,2}. Over 2 million ADEs occur each year, resulting in 100,000 deaths and \$36 million in economic costs³. In recently hospitalized patients, 70% of adverse events that occur within 30 days of discharge are medication related^{4,5}. Of these, at least 58% are preventable and tend to be the result of prescribing or dispensing errors, incomplete drug information, and underuse or overuse of medications^{6,7}.

A number of studies have demonstrated that patients are usually discharged from hospital on substantially different medication regimens than those prior to admission. However, discharge prescriptions are typically not well followed in the community post discharge. We have further explored this phenomenon through secondary analysis of data from a randomized controlled trial (RCT) recently conducted by our study team at the McGill University Health Centre (MUHC), which evaluated the impact of electronic medication reconciliation on ADEs post hospital discharge. Our analyses suggested that 54% of study patients were non-adherent to at least 1 in-hospital medication change, and that patients who were non-adherent to 4 or more in-hospital medication changes experienced a 64% increased risk of emergency department visits and hospital re-admissions compared to those who were adherent to all changes (Figure 1). Furthermore, analyses of patient interview data suggested that unclear communication with patients about medication changes and the reasons for these changes may be driving non-adherence, as might difficulties in managing complex drug regimen information and dosing schedules (data from in-progress manuscript). There is therefore a clear need to implement and evaluate patient support mechanisms that reduce non-adherence to essential changes in therapy following hospitalization.

Figure 1. Impact of non-adherence to in-hospital medication changes on ED visits and hospital re-admission 30 days post discharge.

Objective

The objective of this project is to evaluate the usability and efficacy of a mobile application aimed at improving medication management and subsequent adherence to in-hospital medication changes among high risk patients.

Methodology

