We will conduct an RCT that will assess the usability of a medication management mobile application and its efficacy in decreasing non-adherence to in-hospital medication changes among patients in the internal medicine ward of the Royal Victoria and Montreal General sites of the MUHC. One hundred patients will be randomized 1:1 to either the intervention arm, in which they will receive access to the mobile app, or the control arm, in which they will receive usual care (i.e., no medication management support). We will conduct a usability assessment at hospital discharge (baseline) and at 1 week post-discharge to obtain patient feedback on the app (via a technology acceptance questionnaire) and to document usability using the “think aloud” protocol^{8,9}. We will also compare, between the 2 arms, the rates of non-adherence to treatment changes in the 30-days post-discharge.

Study population

The study population will comprise 100 patients who are discharged from the internal medicine unit of the Royal Victoria and Montreal General sites of the MUHC. To be eligible for participation in the trial, patients must also be covered by the Quebec public insurance drug plan (i.e. they are 65 years or older, are recipients of social assistance, or do not have private drug insurance), must be 18 years or older at the time of admission, must own a tablet, smartphone, desktop PC, or portable computer, must have internet connection on their tablet/smartphone/laptop/PC, must speak and read either English or French, must not be discharged to a rehabilitation or long-term care center, and must have a prognosis of more than 3 months.

Patients who are cognitively impaired or otherwise unable to provide consent will be eligible for inclusion in the study if surrogate consent is granted by a legally authorized representative and if a caregiver has agreed to use the app on the patient’s behalf. Similarly, patients who are completely dependent on a caregiver but capable of providing consent will be enrolled only if the caregiver has agreed to use the app.

Participant recruitment, consent, and enrollment

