The RCT will be conducted at the internal medicine unit of the Royal Victoria and Montreal General sites of the MUHC over a period of 1.5 years (Figure 2). Following approval of the study by the MUHC's institutional review board, study coordinators will begin recruiting, consenting, enrolling, and randomizing eligible patients who are admitted to the internal medicine unit of the MUHC Glen site. Based on recruitment rates from our recently completed trial which was also conducted at the MUHC, we expect this process to take approximately 5-6 months. At discharge, the study coordinator will provide enrolled patients in the intervention arm with access to the mobile application, enter their discharge prescription into the app, acquaint them with and train them in the various features of the app, and conduct a baseline usability assessment.

One week following discharge, study coordinators will conduct usability assessments at patients' homes. Assessment of non-adherence will be conducted by a data analyst at the MCHI Research Group using data from the RAMQ feed and patients' discharge prescriptions. Subsequent data analyses will be conducted over a period of 4 months, beginning 30 days following the enrollment of the last study patient. All data will be stored on a secure server at the MCHI centre, which can only be accessed using employee

identification cards. Following data analysis, an evaluation report will be disseminated to relevant stakeholders at the MUHC (e.g. Committee of Quality and Risk), and a manuscript will be prepared for potential publication in a peer-reviewed journal.

Figure 2. Gantt Chart.

Data storage, privacy, and confidentiality

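### The only efficacy test leaves each patient's number of in-hospital medication changes unused; adjusting for it needs no new data and may add power

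*Combined protocol and SAP*

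**What the plan says.** The Data Analysis section plans descriptive summaries and then one inferential efficacy comparison: "the average number of in-hospital medication changes not adhered to in the 30-day follow-up period using the Student's t-test". It names no covariate, offset, proportion or model. The descriptive output covers "the frequency of nonadherence events (as defined in the previous section) in the 30 days post-discharge, overall and in each study group"; the number of changes made is not named.

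That number will nonetheless be available. Under Data sources, "Medications prescribed at discharge and in-hospital medication changes will be determined using patients' discharge prescriptions". By the outcome definition, each event is a failure on one particular new, stopped or dose-modified drug, so a patient's count cannot exceed that patient's number of changes.

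Methodology announces a comparison of "the rates of non-adherence to treatment changes in the 30-days post-discharge" and does not define a rate. It can be read as events per patient over the common 30 days. This is a gap in wording, not a contradiction of the Data Analysis section.

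**The concern.** A patient with eight changes has more chances to miss one than a patient with two. If the number of changes varies much between patients and is correlated with the number missed, part of the spread in the outcome is explained by a variable already in the data set. An unadjusted t-test leaves that part in the standard error.

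The trial has 100 patients, and the documents give no power calculation, effect size or standard deviation. Using a covariate already in hand is the cheapest way to gain precision. Reporting the number of changes by arm would also show whether the arms had equal opportunity for events.

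**Working it through.** **Inputs from the documents.** 100 patients randomised 1:1, so 50 per arm; 30-day follow-up; and, from Background, "54% of study patients were non-adherent to at least 1 in-hospital medication change". There is no planned power figure to reproduce.

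**Assumptions.** Two-sided 5% level; no dropout; the distribution of the number of changes K; the within-patient correlation of misses (rho); the true effect. Background also reports that "patients who were non-adherent to 4 or more in-hospital medication changes experienced a 64% increased risk", but this describes changes missed, not changes made, and the size of that group is not given.

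**1. How the gain arises.** Let Y be the number missed and p the risk per change, constant, with rho = 0. Then Var(Y) = E[K]p(1-p) + p²Var(K), and the share explained by K is R² = p²Var(K)/Var(Y).

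- Take K = 1 + Poisson(3), so mean 4 and variance 3. With p = 0.189, P(Y ≥ 1) = 1 - (1-p)exp(-3p) = 1 - 0.811 × 0.567 = 0.54, which matches Background.
- Var(Y) = 4 × 0.189 × 0.811 + 0.189² × 3 = 0.613 + 0.107 = 0.720, so SD = 0.85 and R² = 0.107/0.720 = 0.15.
- For a far wider spread (mean 8, variance 56, p = 0.128): Var(Y) = 0.893 + 0.918 = 1.811, so R² = 0.51.

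The difference detectable with 80% power is (1.96 + 0.84) × √[(2/50)(1 - R²)] SD: 0.56 at R² = 0, 0.53 at 0.1, 0.47 at 0.3 and 0.40 at 0.5.

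**2. Main simulation.** There were 24 settings with 10,000 trials each. K was negative binomial with mean (SD) 3 (2), 4 (3), 6 (4) or 9 (5); rho was 0, 0.1 or 0.3; the risk per change was constant or fell as K^-0.5. Misses were beta-binomial, with the control arm calibrated to 54%. The t-test was compared with a linear model on arm and K with HC3 standard errors.

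| Risk per change | Variance falls | Power at rate ratio 0.5: t-test; adjusted | Change (points) | Power at rate ratio 0.6: t-test; adjusted | Change (points) |
|---|---|---|---|---|---|
| Constant (12 settings) | 10-31% | 0.496-0.708; 0.518-0.817 | +2.1 to +12.8 | 0.328-0.482; 0.343-0.607 | +1.5 to +13.7 |
| Falling (12 settings) | 2-11% | 0.514-0.740; 0.507-0.767 | -0.7 to +3.5 | 0.344-0.521; 0.335-0.541 | -0.9 to +2.7 |

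- The median change over all 24 settings was +3.0 points at rate ratio 0.5 and +2.3 at 0.6. Three of 24 were negative at each.
- In patients, a 31% fall in variance is worth 100/0.69 - 100 ≈ 45 extra; a 2% fall is worth 100/0.98 - 100 ≈ 2.
- Type I error was 4.5-5.3% for the t-test and 4.2-5.1% adjusted. Coverage of the adjusted 95% interval was 95.0-95.9%.

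**3. What drives the gain.** It follows the control-arm correlation r between changes made and changes missed. At rate ratio 0.5:

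- r 0.20-0.25: -0.7 to +0.7 points
- r 0.28-0.38: +1.2 to +3.5
- r 0.41-0.47: +3.4 to +5.4
- r 0.50-0.62: +7.4 to +12.8

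**4. A restricted set.** Keep only settings in which at least 5% of controls miss four or more changes (5% is an assumption). The change is then +1.5 to +10.1 points with constant risk (7 settings) and -0.9 to +1.3 with falling risk (4 settings).

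**5. Other distributions.** In 15 further settings (K = 1 + Poisson or negative binomial, mean 4, 6 or 8, constant risk, rate ratio 0.6), R² was 0.08-0.51 and the gain with HC3 was about 0 to 21 points. A quasi-Poisson model with log K as offset and model-based standard errors reached a type I error of 12.4%, so the form of adjustment matters.

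**6. If allocation shifted K.** The intervention arm was given 10% or 20% more changes, with no effect on risk per change (8 settings, rho 0.1).

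- The t-test rejected in 4.8-12.0% of trials, with a spurious difference of 0.04 to 0.23 changes. The adjusted model rejected in 4.3-4.8%, within 0.01 of zero.
- With an unmeasured factor driving both K and risk, the bias was +0.11 to +0.23 unadjusted and -0.03 to -0.08 adjusted.

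**The case against.** The t-test is valid, the documents make no power claim that it fails to meet, and the section on pilot-testing the app calls this a pilot trial. On that view, preferring a covariate-adjusted model is a matter of taste. It is true that there is no bias or contradiction here, and the point should be rated accordingly.

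The benefit is not established by the documents. The top of the range comes from favourable assumptions: in a rerun at rate ratio 0.5, the largest gain (+13.2) had no within-patient correlation and only 2.6% of controls missing four or more changes. With falling risk and the 5% restriction, the gain is essentially nil. This stands, and the median is a fairer summary than the maximum.

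The number of changes could be reported among the clinical characteristics that the plan will summarise. It is not excluded, but it is not named either.

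The most serious objection is that the covariate may be fixed after randomisation. Project timeline lists "recruiting, consenting, enrolling, and randomizing eligible patients who are admitted to the internal medicine unit of the MUHC Glen site", changes are settled at discharge, and "study participants and personnel will not be blinded to group allocation, but data analysts will be". That risk is real. However, app access starts only at discharge, so an effect of allocation on the number of changes is not expected. If there were one, the unadjusted count would be distorted too, and in the settings checked by more. Neither analysis is immune, so both results and the by-arm table are needed.

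**Conclusion.** The concern holds as a minor point of efficiency. The planned test is valid but discards a covariate that bounds the outcome and is already collected. Under the stated assumptions, adjustment changes power by about -1 to +14 points, with a median of +2 to +3. Modelled losses stayed below 1 point in the main simulation and occurred only where r was 0.25 or less; at 0.37 or more the gain was at least 1.5 points. The conclusion that adjustment may help does not depend on one setting. Its size does: it rests on the assumed distribution of changes, the within-patient correlation, and how risk per change varies with the number of changes.

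**What to change.** In Data Analysis, pre-specify the following.

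- **Main comparison:** a linear model of the number of changes not adhered to on arm and number of in-hospital changes (new, stopped, dose modified), with HC3 standard errors and a 95% confidence interval. This keeps the plan's own effect measure, the difference in mean count. Avoid an offset model with model-based standard errors.
- **Covariate:** counted by the blinded data analyst from the chart discharge prescription, in the same way in both arms, and not updated for prescription changes made later through the app.
- **Patients:** all randomised patients with outcome data; those with no changes count as 0.
- **Supporting output:** the unadjusted t-test, the number of changes by arm, and changes not adhered to divided by changes made, the last as a descriptive figure only.

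In Methodology, state that the rate is the number of changes not adhered to per patient over 30 days.

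Before finalising, estimate r in the team's earlier trial, where non-adherence to in-hospital changes has already been analysed.

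The cost is one paragraph and a few lines of SAS, with no new data, visits or patients. The downside is a possible gain of about zero, or a loss of about 1 point of power in the worst modelled case.
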